10.7.1 Objective Response Rate (ORR)

ORR is defined as the proportion of the subjects in the analysis population who have a CR or PR. Responses are based on assessments per RECIST 1.1.

10.7.2 Progression-Free Survival (PFS)

PFS is defined as the duration of time from the first day of trial treatment to the first documented disease progression per RECIST 1.1 or death due to any cause, whichever occurs first.

10.7.3 Disease Control Rate (DCR)

DCR is defined as the percentage of subjects who have achieved CR, PR, and SD. Responses are based on assessments per RECIST 1.1.

10.7.4 Overall Survival (OS)

OS is defined as the time from first dose of study medication to death due to any cause.

Safety

10.7.5 Safety Endpoints

The safety analysis will be based on subjects who experienced toxicities as defined by CTCAE criteria. Safety will be assessed by quantifying the toxicities and grades experienced by subjects who have received the study drug, including serious adverse events (SAEs) and events of clinical interest (ECIs).

Safety will be assessed by reported adverse experiences using CTCAE, Version 4.0. The attribution to study treatment, time-of-onset, duration of the event, its resolution, and any concomitant medications administered will be recorded. AEs will be analyzed including but not limited to all AEs, SAEs, fatal AEs, and laboratory changes.

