2.2 Secondary Objectives & Endpoints

*Note: The secondary objects only apply for patients who are initiated on treatment with an OncoTreat-prioritized FDA-approved or early-phase investigational drug.

2.2.1 Objectives:

The secondary objectives of this study are to:

- To describe the safety and tolerability of using OncoTreat to inform rational treatment decision in subjects with advanced PDA who have progressed on one or two prior lines of therapy.
- To assess the efficacy of OncoTreat by estimating the disease control rate (DCR) at 16 and 24 weeks, the median progression-free survival (PFS), the overall survival (OS), and the CA 19-9 tumor marker response.
- To assess the pharmacokinetics of each OncoTreat-prioritized agent in subjects with advanced PDA.

2.2.2 Endpoints:

Secondary endpoints of interest include:

- Safety/tolerability
 - Incidence of Grade 3/4 adverse events (AEs) in terms categorized and graded according to the National Cancer Institute Terminology Criteria for Adverse Events (NCI CTCAE v4.0).
 - Incidence of dose modifications, interruptions, and discontinuations.
 - Note: OncoTreat-prioritized agents will be dosed at the FDA-approved dose (if available) or the recommended phase 2 dose for investigational agents. Safety endpoints as they pertain to specific drugs will not be assessed in this prospective study, as only a very small number of patients will be assigned to any one of these drugs, all of which are FDAapproved or have been studied in early phase clinical trials and have track records of safety/tolerability.
- DCR, defined as the proportion of subjects with a complete or a partial response as the best response or stable disease, according to RECIST v1.1 criteria.
- PFS, defined as the time from first dose of OncoTreat-prioritized drug to the first occurrence of disease progression or death from any cause (whichever occurs first), using RECIST v1.1 criteria.
- OS, defined as the time from first dose of OncoTreat-informed study drug to death due to any cause.
- Tumor marker response of CA 19-9, defined as ≥ 50% in CA 19-9 in relation to the baseline level at least once during the treatment period.
- Serum concentration or PK parameters for each OncoTreat-prioritized agent.
- Relationship between serum concentration or PK parameters and endpoints of interest.

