4.2 Number of Patients

Thirty subjects will be enrolled on Part 1 and, therefore, up to a maximum of 30 subjects will receive OncoTreat-prioritized agents on Part 2. No subjects will be replaced.

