10.2 Definitions

Evaluable for toxicity: All patients will be evaluable for toxicity from the time of their first treatment with an OncoTreat-prioritized agent.

Evaluable for objective response: Only those patients who have measurable disease present at baseline, have received at least one cycle of therapy, and have had their disease re-evaluated will be considered evaluable for response. These patients will have their response classified according to the definitions stated below. (*Note*: Patients who exhibit objective disease progression prior to the end of cycle 1 will also be considered evaluable.)

Evaluable for feasibility – primary outcome: All subjects who receive a single dose of study drug will be included in the primary outcome analysis of feasibility.

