12. STATISTICAL CONSIDERATIONS

This is a single arm, phase Ib study with 2 co-primary endpoints:

- Feasibility: The primary objective of this trial is to determine the feasibility of the OncoTreat platform in guiding therapy. The primary outcome is whether a subject begins therapy on Part 2. Previous attempts to match subjects based on DNA profiling have yielded enrollment rates of 3-5% [14, 78]. We hypothesize that we will validate OncoTreat matches for 50% of subjects and that at least 30% of enrolled subjects (60% of matches) will begin therapy on Part 2. With 30 enrolled patients on Part 1, we will have 80% power to detect a treatment rate of 30% on Part 2 compared to a historical treatment rate of 5% with alpha of 0.05. We will also assess the "match rate" the fraction of patients who match with at leaset one drug. With 30 enrolled subjects, we will have 97% power with alpha = 0.05 to detect a 50% match rate (15 of 30 subjects) compared to a (liberal) estimated match rate of 20% based on DNA profiling in PDA.
- Efficacy: The primary clinical efficacy endpoint is the **objective response rate (ORR)** for OncoTreat-prioritized drugs, which corresponds to the number of patients whose tumors demonstrate a 30% or greater reduction from baseline in the sum of the diameters of all target lesions amongst all evaluable patients, as assessed by standard-of-care CT scans. We target estimating the ORR and the corresponding 95% confidence interval.

Secondary endpoints will include: 1) **disease control rate (DCR) at 16 and 24 weeks**, which corresponds to the number of patients whose tumors demonstrate either an objective response or stable disease, defined as a no more than 20% increase from baseline in the sum of the diameters of all target lesions; 2) **median progression-free survival (mPFS)**, defined as the median duration prior to the development of disease progression or patient death; 3) **overall survival (OS)**, defined as time from first dose of OncoType-informed drug to death due to any cause; and 4) **safety and tolerability**, defined as the incidence of Grade 3/4 AEs in terms categorized and graded according to NCI CTCAE v4.0. We will estimate DCR, mPFS, and OS and their 95% confidence interval.

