The phase III trial (NAPOLI-1) that resulted in the FDA-approval of nanoliposomal irinotecan and 5-fluorouracil in the second-line setting demonstrated a median overall survival of 6.1 months versus 4.2 months for 5-fluorouracil monotherapy (primary endpoint), mPFS of 3.1 months, and an ORR of 16% (compared to 1% in the 5-fluorouracil arm) [7]. Fifty-one (12%) patients had not had previous treatment for metastatic disease, 234 (56%) had received one previous line of metastatic treatment, and 132 (32%) had previously received two or more lines of metastatic treatment. The disease control rate was less than 20% and did not differ between treatment groups. Thus, based on historical controls, the ORR for treatment-resistant metastatic PDAC is expected to be no more than 16%.

Using the above mentioned rates, a sample size of n = 9 achieves at least a 80% power to detect a difference of 25% in ORR (30% vs 5%) using a one-sided binomial test with a target alpha of 0.1. To be conservative, we use the minimum number of patients (9) expected to be treated in this calculation. If at the end of the study the total number of objective responses is greater than or equal to 2, we will be able to reject the historical rate of 5% at the significance level of 0.05 with power of 69% and OncoTreat will have demonstrated a clear signal of clinically meaningful improvement in the primary endpoint for patients with advanced, previously-treated PDA. Assuming about 30% of enrolled patients will receive an OncoTreat-informed treatment, N = 30 subjects is an appropriate sample size for this prospective study.

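### The first sentence of Section 10.7.5 selects the safety analysis set on having had a toxicity, against Sections 10.2 and 2.2 and its own next sentence, and Section 12 does not settle the denominator

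*Combined protocol and SAP*

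**What the plan says.** Five places bear on who is counted for safety.

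- **Section 10.7.5, first sentence:** "The safety analysis will be based on subjects who experienced toxicities as defined by CTCAE criteria".
- **Section 10.7.5, second sentence:** safety is assessed by "quantifying the toxicities and grades experienced by subjects who have received the study drug".
- **Section 10.2:** "All patients will be evaluable for toxicity from the time of their first treatment with an OncoTreat-prioritized agent".
- **Section 2.2, opening note:** the secondary objectives, safety among them, "only apply for patients who are initiated on treatment with an OncoTreat-prioritized FDA-approved or early-phase investigational drug".
- **Section 12:** safety and tolerability are "defined as the incidence of Grade 3/4 AEs in terms categorized and graded according to NCI CTCAE v4.0". No analysis set or denominator is given.

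The endpoint in Section 2.2.2 is likewise an incidence, "Incidence of Grade 3/4 adverse events (AEs) in terms categorized and graded according to the National Cancer Institute Terminology Criteria for Adverse Events". A second safety endpoint there is the incidence of dose modifications, interruptions and discontinuations. Neither entry states its denominator.

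**The concern.** The wording of the first sentence of 10.7.5 is that of an analysis population: it says which subjects the analysis rests on. Taken at its word, a treated subject with no toxicity is not in the safety analysis.

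The endpoint is an incidence, so the denominator is part of its definition. Conditioning on having had a toxicity removes only subjects who could not have contributed an adverse event. Adverse event rates can then only stay the same or rise. The trial expects few treated subjects, so each one left out counts.

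The second safety endpoint is exposed in a different way. A subject without toxicity who stops treatment for another reason, such as progression, would leave both the numerator and the denominator of the discontinuation rate.

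**Working it through.** **Is there a figure to reproduce?** The documents give no adverse event rate, safety sample size or safety precision. The only usable figure is the number treated. Section 12 expects 30% of 30 enrolled to start therapy: 0.30 × 30 = 9. By the other route, 50% of 30 match and 60% of those start: 0.60 × 15 = 9. Both agree with Section 12, where "we use the minimum number of patients (9) expected to be treated in this calculation". The upper bound is in Section 4.2: "up to a maximum of 30 subjects will receive OncoTreat-prioritized agents on Part 2".

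**Formula.** Let n be the number treated, m the number of those with at least one toxicity, and x the number with the adverse event of interest. Assume that every subject with that event counts as having a toxicity.

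- Rate on treated subjects: x/n.
- Rate on subjects with a toxicity: x/m.
- Ratio for x > 0: (x/m) ÷ (x/n) = n/m, which is at least 1. For x = 0 both rates are zero.
- Any-toxicity rate on the restricted set: m/m = 100%, whatever the drugs do.

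**Nine treated, x = 3 with a Grade 3/4 event** (x and m are assumptions; exact 95% intervals):

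| m with any toxicity | x/m | 95% interval | n/m |
|---|---|---|---|
| 9 | 33.3% | 7.5 to 70.1% | 1.00 |
| 8 | 37.5% | 8.5 to 75.5% | 1.125 |
| 7 | 42.9% | 9.9 to 81.6% | 1.29 |

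The rate on all treated subjects is 3/9 = 33.3% in every row.

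**Thirty treated, x = 10** (again assumed): 10/30 = 33.3% on treated subjects. On the restricted set it is 10/27 = 37.0% if three have no toxicity, and 10/24 = 41.7% if six have none.

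**How likely is no distortion at all?** The two sets coincide only if every treated subject has a toxicity. The documents give no per-subject probability q, so a range is shown. With subjects taken as independent, the chance that all 9 have one is q⁹:

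- q = 0.80: 13%
- q = 0.90: 39%
- q = 0.95: 63%
- q = 0.99: 91%

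**Discontinuations.** Here n/m does not apply, because a subject without toxicity can have the event. Suppose 9 are treated, 1 has no toxicity and 4 discontinue (assumed). The treated-set rate is 4/9 = 44.4%. On the restricted set it is 3/8 = 37.5% if the subject without toxicity is one of the four, and 4/8 = 50.0% if not. The error can go either way.

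**The case against.** The best defence is that this is one loose sentence in a plan that otherwise points to treated subjects. Section 10.2 is where the protocol defines its evaluability sets, and it includes everyone treated. The scope note in 2.2 and the second sentence of 10.7.5 agree, and Section 11.3 has the monitoring committee follow every treated subject for toxicity. The disputed sentence does not use the words denominator, population or analysis set, and may only mean that the safety data are CTCAE-graded toxicities.

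Much of this stands. A reader might infer that the plan is committed to a denominator restricted to subjects with toxicity and so inflates every adverse event rate. The documents do not support that. The section is internally inconsistent, not committed to one rule. Inflation also needs two conditions: the sentence is applied as the denominator, and at least one treated subject has no toxicity. Zero-event rates never move.

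The size may also be small. Section 8.1.1 counts adverse events whether or not they are related to participation, and Section 8.2.4 adds laboratory abnormalities. If toxicities means all of these, few patients with advanced pancreatic cancer may have none; that is a judgement, since no rate is given. With one such subject among nine, the shift from 33.3% to 37.5% is small against an interval of 7.5 to 70.1%.

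Nor does any stated decision turn on the rate. The safety objective is descriptive, and the stopping rules in Section 10.11 set no numerical event rate. Section 8.4 requires all adverse events in the study period to be recorded, so the rate on treated subjects can always be computed.

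What the defence does not do is remove the conflict. The sentence stands in the section that describes the safety analysis, and Section 12, where an analyst would look for the answer, gives none.

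**Conclusion.** The point holds as a contradiction that should be corrected. Followed literally, the first sentence of 10.7.5 gives a wrong Grade 3/4 incidence whenever such an event occurs and some treated subject has no toxicity. It also fixes the any-toxicity rate at 100%. It conflicts with Section 10.2, the scope note in 2.2 and the sentence that follows it.

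With the expected 9 treated, the multiplier on nonzero adverse event rates is 1.00, 1.125 or 1.29 for zero, one or two subjects without toxicity. These counts, and the 3 Grade 3/4 cases used to illustrate them, are assumptions. The multiplier also assumes that anyone with the event counts as having a toxicity.

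The consequence is limited to the reporting of a descriptive secondary endpoint. No hypothesis test or numerical stopping threshold depends on it.

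**What to change.** Replace the first sentence of Section 10.7.5 with: *The safety analysis population is all subjects who received at least one dose of an OncoTreat-prioritized agent.*

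Then state in Sections 10.7.5 and 12 that this population is the denominator for adverse event incidence and for the incidence of dose modifications, interruptions and discontinuations.

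This matches Section 10.2 and the scope note in 2.2. It costs two or three sentences, needs no new data collection, and leaves sample size, power, alpha and clinical conduct as they are.

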10.8 Pharmacokinetic Outcome Measures

Pharmacokinetic (PK) samples will be collected for all subjects (see Appendix _____ for sample collection details) and include the following:

10.9 Analysis of Exploratory Endpoints

10.10 Unblinding Procedures

Not applicable – this is not a blinded study.

10.11 Stopping Rules

Early trial termination will be the result of the criteria specified below:

- Quality or quantity of data recording is inaccurate or incomplete
- Poor adherence to protocol and regulatory requirements
- Incidence or severity of adverse drug reaction in this or other studies indicates a potential health hazard to subjects
- Plans to modify or discontinue the development of the study drug

11. DATA REPORTING / REGULATORY REQUIREMENTS

Adverse event lists, guidelines, and instructions for AE reporting can be found in Section 8 (Adverse Events: List and Reporting Requirements). The Data Safety Monitoring Plan is described in Section 11.3.

11.1 Data Collection

The Herbert Irving Comprehensive Cancer Center has an electronic clinical trials and data management system (CTMS) that will be used for data collection. CRFs for the study will be built into the CTMS, Velos, for data entry. The system has full auditing capabilities which is web-based and housed on a server in a fully HIPAA compliant server room with restricted access and video camera monitoring. All users must login with their own application username and password. Users off campus must first access the Virtual Private Network with their assigned campus username and password and then use their application credentials. Users are only able to see study information if they are indicated as study personnel in our electronic IRB system. Users are limited to access based on the role assigned in their corresponding protocol. Subject data is entered directly into the system, which (in the case of Columbia subjects) confirms the correct identity of patients via an interface with the electronic medical patient index. Staff with the appropriate IRB defined roles can run reports within the system for reporting purposes.

11.2 Data Reporting

Case Report Forms (CRFs) will be completed for each subject enrolled into the clinical study through the CTMS. It is the investigator's responsibility for ensuring that all clinical and laboratory data entered on the corresponding CRFs are complete, accurate and authentic.

11.3 Data and Safety Monitoring Committee

The NCI-approved Data Safety and Monitoring Committee (DSMC) of the Herbert Irving Comprehensive Cancer Center (HICCC) will monitor every subject who receives treatment on this protocol for toxicity. This protocol will adhere to the policies of the currently approved HICCC Data and Safety Monitoring Plan (DSMP), which is in accordance with NCI and CUMC-IRB policy and guidelines. The committee is chair is appointed by the HICCC Director. The committee consists of HICCC faculty and staff with expertise in oncology, research pharmacy, research nursing, and data management. The DSMC convenes twice a month to review patient safety and the conduct of the trial. The PI will submit data and safety monitoring reports to the DSMC at a frequency to be determined by the DSMC based on risk to the subjects.

At the time of renewal, the study team will submit the most recent DSMC approval letter for safety review to the CUMC IRB. Any modifications that are required by the DSMC to ensure patient safety will be submitted to the IRB. All protocol deviations, violations, and eligibility waivers will be submitted to and approved by the DSMC prior to being reported to the IRB. All study data reviewed and discussed during these meetings will be kept confidential.

11.4 Quality Control and Quality Assurance

Independent monitoring of the clinical study for protocol and GCP compliance will be conducted periodically by the CPDM Compliance Core on behalf of the HICCC DSMC. Additionally, the Compliance Oversight Committee of the IRB at Columbia University Medical Center may audit the study at any time per institutional policies and procedures. The investigator-sponsor and Columbia University Medical Center will permit direct access of the study monitors and appropriate regulatory authorities to the study data and to the corresponding source data and documents to verify the accuracy of this data.

A risk-based approach will be used by the Compliance Core to determine the frequency, number of subject charts, and data elements to be monitored. The Compliance Coordinator will review the study status and summarize enrollment, toxicities, SAEs/UPs, dose escalation, statistical endpoints (e.g., stopping rules), etc. for the full DSMC membership at the regularly scheduled meetings.

Internal On-site Monitoring:

- Initial, recurrent, and close-out on-site monitoring visits will also be conducted at remote clinical sites, as appropriate/feasible. Other sites will have monitoring performed remotely (see below for further details).
- The study Monitoring Visit Log will be completed and signed by the monitor and the PI/CRNP/CRN and/or CRC and will be filed in the regulatory binder.
- The Compliance Coordinator will communicate with the site coordinator/Site Principle Investigator to schedule the monitoring visit and arrange for access to study materials and documentation.
- The assigned Compliance Coordinator will monitor IIT trials within 1 month after the first subject is enrolled and throughout the life of the study to ensure that the study is being conducted in accordance with the protocol, GCP, applicable federal and local regulations, and per all applicable SOPs. The Compliance Coordinator is responsible to notify the PI and CRNP/CRN/CRC of upcoming monitor visits and convey what

information and documentation will be required for the visit(s). The Compliance Coordinator is responsible for verifying that informed consent is properly obtained, eligibility is met (via the central registration process), and all study procedures are conducted according to the study protocol. The Compliance Coordinator will also verify that the data reported in the CRF's accurately reflect source documents, that all toxicities have been reported to date, and that all SAE's/UPs/deviations/violations have been reported according to local IRB and HICCC DSMC requirements. The Compliance Coordinator will issue queries and ensure resolution in a timely and efficient manner. The Compliance Coordinator will also monitor for applicable regulatory compliance and research pharmacy compliance (if applicable) and communicate any deficiencies as appropriate.

11.5 Confidentiality

Information about study subjects will be kept confidential and managed according to the requirements of the Health Insurance Portability and Accountability Act (HIPAA). Those regulations require a signed subject authorization informing the subject of the following:

- What protected health information (PHI) will be collected from subjects in this study
- Who will have access to that information and why
- Who will use or disclose that information
- The rights of a research subject to revoke their authorization for use of their PHI

In the event that a subject revokes authorization to collect or use PHI, the investigator, by regulation, retains the ability to use all information collected prior to the revocation of subject authorization. For subjects that have revoked authorization to collect or use PHI, attempts should be made to obtain permission to collect at least vital status (e.g., that the subject is alive) at the end of their scheduled study period.

The subject binders will be maintained with in the CPDM offices, a secured floor within the Herbert Irving Pavilion and only the investigator and study staff will have access to the file.

